6.1 Lateral Rectus Recession Plus Medial Rectus Resection

Participants in this arm underwent unilateral horizontal strabismus surgery consisting of lateral rectus recession combined with medial rectus resection. The lateral rectus muscle was weakened by recession, and the medial rectus muscle was strengthened by resection. In the resection procedure, the medial rectus muscle was isolated, disinserted, shortened by removing a measured segment according to the planned

surgical dosage, and reattached to the sclera. Surgical dosage was determined according to the preoperative distance deviation angle.

6.2 Lateral Rectus Recession Plus Medial Rectus Plication

Participants in this arm underwent unilateral horizontal strabismus surgery consisting of lateral rectus recession combined with medial rectus plication. The lateral rectus muscle was weakened by recession, and the medial rectus muscle was strengthened by plication. In the plication procedure, the medial rectus muscle was folded and sutured to strengthen the muscle without complete disinsertion from its original scleral insertion. Surgical dosage was determined according to the preoperative distance deviation angle.

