3.2 Secondary Objectives

- To compare postoperative ocular alignment between the two surgical groups.
- To compare surgical success at postoperative month 3 between the two surgical groups.
- To evaluate time-dependent changes in accommodative amplitude during postoperative follow-up.

4. Study Design

This is a prospective, interventional, non-randomized, parallel-group comparative clinical study conducted at a single tertiary ophthalmology center. Participants with primary exotropia were assigned to one of two surgical groups. The study compared unilateral lateral rectus recession plus medial rectus resection with unilateral lateral rectus recession plus medial rectus plication.

Participants were allocated using an alternating sequential allocation method according to the order of enrollment. The first participant who consented to participate was assigned to the LRR+MRR group, the second participant was assigned to the LRR+MRP group, and subsequent participants were assigned alternately thereafter. No random sequence generation, allocation concealment, or randomization procedure was used.

5. Study Population

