5.1 Inclusion Criteria

- Patients aged 5 to 40 years.
- Diagnosis of basic primary exotropia.
- Stable deviation angle over three consecutive preoperative visits.
- Deviation angle of at least 20 prism diopters.
- Literacy and cooperation sufficient to perform accommodative amplitude testing.
- Agreement to undergo unilateral horizontal strabismus surgery.
- Written informed consent obtained from the participant and/or legal guardian.

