8.2 Secondary Outcome Measures

- Ocular alignment: Ocular deviation in primary position was measured using the prism and alternate cover test. Distance and near deviation angles were recorded in prism diopters at baseline and during postoperative follow-up.

- Surgical success: Surgical success was assessed at postoperative month 3 and was defined as ocular deviation in primary position of 10 prism diopters or less of exotropia or 5 prism diopters or less of esotropia.

9. Sample Size

A prior sample size calculation was performed based on the expected between-group difference in operated-eye change in accommodative amplitude from baseline to postoperative week 1, which was considered the primary functional outcome for sample size planning. Assuming a two-sided alpha level of 0.05, 80% power, an anticipated mean difference of 0.7 diopters, and a common standard deviation of 0.97 diopters, the minimum required sample size was estimated to be 31 patients per group. To allow for possible loss to follow-up, at least 36 patients were considered necessary in each group. The final analysis included 85 patients: 40 in the LRR+MRR group and 45 in the LRR+MRP group.

10. Statistical Analysis Plan

All statistical analyses will be performed using IBM SPSS Statistics version 28.0. Continuous variables will be assessed for normality using the Shapiro-Wilk test. Normally distributed continuous variables will be presented as mean \pm standard deviation. Non-normally distributed continuous variables will be presented as median and range. Categorical variables will be presented as number and percentage.

Between-group comparisons of continuous variables will be performed using the Mann-Whitney U test when variables are not normally distributed. Comparisons among more than two independent groups will be performed using the Kruskal-Wallis test. Repeated measurements within groups will be analyzed using the Friedman test. When significant differences are identified in repeated-measure analyses, pairwise comparisons will be performed using the Wilcoxon signed-rank test with Bonferroni correction.

Associations between categorical variables will be evaluated using the Pearson chi-square test or Fisher exact test, as appropriate. A two-sided p value less than 0.05 will be considered statistically significant.

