The main comparative analysis will evaluate postoperative changes in accommodative amplitude within and between the LRR+MRR and LRR+MRP groups. Secondary analyses will compare ocular alignment and surgical success between groups. Age-stratified analyses may be performed using predefined age categories of 5-12 years, 13-19 years, and 20-40 years, with delta accommodative amplitude used to minimize the effect of age-related baseline differences in accommodation.

11. Ethical Considerations

The study was conducted in accordance with the principles of the Declaration of Helsinki and was approved by the Clinical Research Ethics Committee of Basaksehir Cam and Sakura City Hospital. Written informed consent was obtained from all participants and/or their legal guardians before enrollment. Participation did not change the standard clinical indication for surgery, and both surgical techniques are established procedures used in the management of horizontal strabismus.

12. Data Management and Confidentiality

Study data were collected from ophthalmologic examinations and postoperative follow-up assessments. Data were recorded in a deidentified research dataset for analysis. No names, direct identifiers, or individual participant identifiers are included in this public protocol document.

13. Individual Participant Data Sharing Statement

Individual participant data will not be shared because no specific data-sharing plan was included in the study protocol or informed consent documents.

14. Safety Considerations

Both interventions are standard surgical procedures for horizontal strabismus. Postoperative clinical assessments included best-corrected visual acuity, ocular motility, ocular alignment, and clinical examination. Patients requiring further management after completion of the study follow-up were treated according to routine clinical practice. Patients with residual exotropia of 12 prism diopters or more at postoperative month 3 were scheduled for additional surgery in the fellow eye after completion of the study follow-up period.

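### Extent of surgery follows the preoperative distance angle in both arms, but the between-arm comparison of accommodative change is not adjusted for that angle

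*Combined protocol and SAP*

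**What the plan says.** Sections 6.1 and 6.2 use one sentence for both arms: "Surgical dosage was determined according to the preoperative distance deviation angle". Neither section gives a dosage table or millimetre values, and no section says that the millimetres operated are recorded for the study. Section 5.1 sets only a lower bound for eligibility: "Deviation angle of at least 20 prism diopters".

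Section 4 describes alternation by enrolment order, starting with resection, and states: "No random sequence generation, allocation concealment, or randomization procedure was used". No stratification by angle is mentioned.

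Section 10 defines the main analysis: "The main comparative analysis will evaluate postoperative changes in accommodative amplitude within and between the LRR+MRR and LRR+MRP groups". The between-arm method it names is a rank test: "Between-group comparisons of continuous variables will be performed using the Mann-Whitney U test when variables are not normally distributed". No covariate or regression model appears. The only stratifier is age, and it is optional. Section 7.1 confirms that the distance angle was measured on at least three preoperative visits, so the variable should be available.

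**The concern.** Section 2 argues that technique may affect accommodation because surgery can disturb the anterior ciliary vessels and related neural pathways. On that reasoning, the amount of surgery is a plausible second influence on the primary outcome, although the documents do not say so. Since the amount follows the angle, an imbalance in angle between arms would carry an imbalance in extent of surgery.

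Neither design nor analysis guards against this. Alternation without concealment lets whoever enrols a patient know the next assignment. The analysed arms also do not look like the arms as alternated (see the working). An unadjusted comparison could then mix a difference in extent of surgery with a difference in technique.

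**Working it through.** **1. The plan's own figure.** Inputs from Section 9: difference 0.7 D, SD 0.97 D, two-sided alpha 0.05, power 80%. Normal approximation: n = 2 × [0.97 × (1.960 + 0.842) / 0.7]² = 30.14, rounded up to 31 per group. The stated 31 is reproduced. The 0.97 D and 0.7 D are used below as the scale.

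**2. Analysed counts against alternation.** The first patient went to resection, so at any point the resection arm has as many patients as the plication arm or one more. With 45 plication patients analysed, at least 45 were allocated to resection, and 40 of those were analysed. Either resection lost at least 45 − 40 = 5 more patients than plication, or alternation was not followed. Section 5.2 lists incomplete examinations and loss to follow-up as exclusions, so removal after allocation is possible.

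**3. Chance imbalance in angle, if allocation behaved like a fair one.**
- SE of the standardised gap = √(1/40 + 1/45) = 0.217 SD.
- Median absolute gap = 0.6745 × 0.217 = 0.147 SD.
- 95% limit = 1.96 × 0.217 = 0.426 SD (0.43 rounded).

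**4. Shift in the primary difference.** Shift = r × gap × 0.97 D, where r is the within-arm correlation of angle with amplitude change. The documents give no r, so a range is assumed.

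| r (assumed) | Shift at median gap | Shift at 95% limit | 95% limit as share of 0.7 D |
|---|---|---|---|
| 0 | 0 | 0 | 0% |
| 0.1 | 0.01 D | 0.04 D | 6% |
| 0.2 | 0.03 D | 0.08 D | 12% |
| 0.3 | 0.04 D | 0.12 D | 18% |
| 0.5 | 0.07 D | 0.21 D | 30% |

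For scale, the SE of the unadjusted difference is 0.97 × 0.217 = 0.21 D. The largest shift in the table is therefore about one standard error.

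**5. What it would take to produce the whole planned effect.** Gap = 0.7 / (r × 0.97), which is 2.4 SD at r = 0.3 and 1.4 SD at r = 0.5. Chance imbalance would not do this.

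**6. Effect of adjustment on precision.** Residual SD = 0.97 × √(1 − r²). The required n per group becomes 30 (r = 0.1), 28 (r = 0.3) or 23 (r = 0.5), against 31 unadjusted. By this approximation the covariate needs no added sample.

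These calculations are on the mean scale and only approximate what happens in a Mann-Whitney comparison.

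**The case against.** The strongest reply is that the causal link is inferred. Section 2 ties accommodation to how the muscle is handled and is silent on millimetres. If angle is unrelated to amplitude change, no imbalance matters. This stands, and it is why the range includes r = 0.

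Second, under fair allocation chance imbalance is already part of the sampling error of the unadjusted test, and its overall 5% error rate holds. This also stands. Figures at the 95% limit describe an unlucky trial; at the median gap the shift is at most about 10% of 0.7 D (0.07 / 0.7). The reply is weaker here than in a randomised trial, however, because fair allocation is the favourable assumption in an unconcealed scheme with analysed counts of 40 and 45.

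Third, a reader might infer that the arms received different amounts of surgery for the same angle, or that the plan commits itself to crediting technique with any difference. The documents support neither. Both arms share one dosing sentence, and Sections 3.1 and 10 speak only of comparing and evaluating. The text also does not say that angle alone decided dosage, or how widely dosage varied. If millimetres at a given angle did differ by arm, they could be part of the technique as delivered, and adjusting the main analysis for them would change the question.

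Fourth, Mann-Whitney takes no covariate, and the document postdates the end of the study period and reports the final counts. An adjusted model added now is probably post hoc. This is correct and is reflected in the fix.

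**Conclusion.** The gap is real and moderate. Extent of surgery follows the distance angle in both arms, balance in angle cannot be presumed, and the planned between-arm comparison does not use it. Whether this biases the result depends on two undocumented conditions: that the arms differ in baseline angle, and that angle is related to amplitude change.

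With r assumed between 0 and 0.5 and an imbalance no worse than chance, the shift is 0 to about 0.07 D at the median gap and 0 to 0.21 D at the 95% limit, against the planned 0.7 D. Selective allocation or differential dropout could produce a larger gap; the documents give no basis for sizing that.

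It would go too far to conclude that a technique effect found in this trial is really a dosage effect. The documents show no dosage difference and no dosage effect on accommodation.

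**What to change.** In Section 10:

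- Add a between-arm linear model, or a rank ANCOVA if the residuals call for it, of operated-eye change in accommodative amplitude from baseline to week 1, the endpoint on which Section 9 sized the trial. Put preoperative distance angle in the same model as baseline amplitude and age.
- Label this analysis as specified after data collection, and show it beside the unadjusted test.
- Report baseline distance angle by arm. Where they were recorded, also report millimetres of lateral rectus recession and of medial rectus resection or plication, by arm and by angle.
- If millimetres at a given angle differ by arm, state that the result compares the techniques at the dosages used. Any adjustment for millimetres belongs in a sensitivity analysis only.

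Cost: one degree of freedom for the angle, a model beyond Mann-Whitney, and post hoc status. The angle was already measured. The documents do not say whether millimetres were recorded, so that table depends on the source records. No change to any dosage is proposed.

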6.3 Operative and Postoperative Management

All procedures were planned and performed under general anesthesia by an experienced strabismus surgeon. Postoperative topical moxifloxacin-dexamethasone drops were prescribed and tapered over one month. Postoperative follow-up examinations were performed at week 1, month 1, and month 3.

7. Study Assessments

7.1 Preoperative Ophthalmologic and Strabismus Examination

All participants underwent comprehensive ophthalmologic examination, including cycloplegic refraction, best-corrected visual acuity assessment, slit-lamp examination, dilated fundus examination, axial length measurement, and ocular motility assessment. Distance and near deviation angles were measured in primary position using the prism and alternate cover test, with and without spectacles, on at least three preoperative visits. Refractive data were converted to spherical equivalent. Near deviation was repeated with a +3.00 diopter lens to assess for a high accommodative convergence/accommodation ratio.

7.2 Measurement of Accommodative Amplitude

Accommodative amplitude was measured separately in each eye using the minus lens method by a single investigator. Measurements were performed in a well-lit room with the participant seated comfortably. Participants wore their distance correction when needed, and the fellow eye was occluded during monocular testing. A near acuity chart was held at 33 cm, and participants were asked to read the smallest visible line. Minus lenses were added over the distance correction in 0.25-diopter increments until the target could no longer be read clearly. The highest minus lens power at which clear near vision was maintained was recorded, and 3.00 diopters were added to account for the 33-cm working distance.

7.3 Postoperative Follow-up

Follow-up examinations were performed at postoperative week 1, postoperative month 1, and postoperative month 3. At each visit, best-corrected visual acuity, ocular motility, primary position deviation angle, and accommodative amplitude were recorded.

8. Outcome Measures

8.1 Primary Outcome Measure

Change in accommodative amplitude: Accommodative amplitude was measured separately in each eye using the minus lens method. Measurements were performed before surgery and at postoperative week 1, postoperative month 1, and postoperative month 3. Changes were calculated by comparing postoperative values with the baseline preoperative value and were recorded in diopters.

8.2 Secondary Outcome Measures

- Ocular alignment: Ocular deviation in primary position was measured using the prism and alternate cover test. Distance and near deviation angles were recorded in prism diopters at baseline and during postoperative follow-up.

- Surgical success: Surgical success was assessed at postoperative month 3 and was defined as ocular deviation in primary position of 10 prism diopters or less of exotropia or 5 prism diopters or less of esotropia.

9. Sample Size

A prior sample size calculation was performed based on the expected between-group difference in operated-eye change in accommodative amplitude from baseline to postoperative week 1, which was considered the primary functional outcome for sample size planning. Assuming a two-sided alpha level of 0.05, 80% power, an anticipated mean difference of 0.7 diopters, and a common standard deviation of 0.97 diopters, the minimum required sample size was estimated to be 31 patients per group. To allow for possible loss to follow-up, at least 36 patients were considered necessary in each group. The final analysis included 85 patients: 40 in the LRR+MRR group and 45 in the LRR+MRP group.

10. Statistical Analysis Plan

All statistical analyses will be performed using IBM SPSS Statistics version 28.0. Continuous variables will be assessed for normality using the Shapiro-Wilk test. Normally distributed continuous variables will be presented as mean \pm standard deviation. Non-normally distributed continuous variables will be presented as median and range. Categorical variables will be presented as number and percentage.

Between-group comparisons of continuous variables will be performed using the Mann-Whitney U test when variables are not normally distributed. Comparisons among more than two independent groups will be performed using the Kruskal-Wallis test. Repeated measurements within groups will be analyzed using the Friedman test. When significant differences are identified in repeated-measure analyses, pairwise comparisons will be performed using the Wilcoxon signed-rank test with Bonferroni correction.

Associations between categorical variables will be evaluated using the Pearson chi-square test or Fisher exact test, as appropriate. A two-sided p value less than 0.05 will be considered statistically significant.

The main comparative analysis will evaluate postoperative changes in accommodative amplitude within and between the LRR+MRR and LRR+MRP groups. Secondary analyses will compare ocular alignment and surgical success between groups. Age-stratified analyses may be performed using predefined age categories of 5-12 years, 13-19 years, and 20-40 years, with delta accommodative amplitude used to minimize the effect of age-related baseline differences in accommodation.

11. Ethical Considerations

The study was conducted in accordance with the principles of the Declaration of Helsinki and was approved by the Clinical Research Ethics Committee of Basaksehir Cam and Sakura City Hospital. Written informed consent was obtained from all participants and/or their legal guardians before enrollment. Participation did not change the standard clinical indication for surgery, and both surgical techniques are established procedures used in the management of horizontal strabismus.

12. Data Management and Confidentiality

Study data were collected from ophthalmologic examinations and postoperative follow-up assessments. Data were recorded in a deidentified research dataset for analysis. No names, direct identifiers, or individual participant identifiers are included in this public protocol document.

13. Individual Participant Data Sharing Statement

Individual participant data will not be shared because no specific data-sharing plan was included in the study protocol or informed consent documents.

14. Safety Considerations

Both interventions are standard surgical procedures for horizontal strabismus. Postoperative clinical assessments included best-corrected visual acuity, ocular motility, ocular alignment, and clinical examination. Patients requiring further management after completion of the study follow-up were treated according to routine clinical practice. Patients with residual exotropia of 12 prism diopters or more at postoperative month 3 were scheduled for additional surgery in the fellow eye after completion of the study follow-up period.

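### No covariate-adjusted between-group analysis of the primary outcome is planned, although allocation was open alternation across ages 5 to 40 and baseline amplitude and age are recorded

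*Combined protocol and SAP*

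**What the plan says.** Section 4 describes strict alternation by enrolment order, the first patient going to resection, and adds: "No random sequence generation, allocation concealment, or randomization procedure was used". Section 5.1 admits patients aged 5 to 40. Section 8.1 has amplitude measured in each eye before surgery and at three postoperative visits, with the outcome expressed as change from the preoperative value in dioptres.

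Section 9 sizes the study on operated-eye change from baseline to week 1, with "an anticipated mean difference of 0.7 diopters, and a common standard deviation of 0.97 diopters".

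On analysis, section 10 states: "Between-group comparisons of continuous variables will be performed using the Mann-Whitney U test when variables are not normally distributed". It names no two-group test for normally distributed data, no model with covariates, and no between-group effect estimate with a confidence interval. Section 10 also says that age-stratified analyses in three bands may be done, "with delta accommodative amplitude used to minimize the effect of age-related baseline differences in accommodation".

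**The concern.** Under open alternation, whoever enrols the next patient can know which technique comes next, so the design does not protect baseline balance. Section 10 itself recognises that accommodation at baseline varies with age.

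Subtracting baseline removes a baseline difference from the comparison only if the amount of change is unrelated to baseline amplitude and age. If patients with more accommodation lose more of it, a younger arm shows a larger mean loss with no difference between techniques. Optional strata do not answer this, because they need not be done and give no pooled adjusted estimate.

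Two things are at stake. One is possible bias in the primary comparison if the arms differ in age or baseline amplitude. The other is precision, because variation that the recorded predictors could explain stays in the error term. In addition, a Mann-Whitney p value alone gives no estimate to set against the 0.7 D on which the study was sized.

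**Working it through.** **Inputs from the documents.** Two-sided alpha 0.05, power 80%, difference 0.7 D, SD of change 0.97 D, 31 per group, and 40 and 45 patients analysed (section 9).

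**Inputs assumed, not in the documents.** Ages spread evenly over 5-40 (SD 35/√12 = 10.1 years). Amplitude falls 0.2 D per year with residual SD 1.5 D, so baseline SD = √((0.2 × 10.1)² + 1.5²) ≈ 2.5 D. Patients lose a fraction L of baseline amplitude, with L between 5% and 20%. For the biased case, one arm is 3.5 years younger.

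**1. The plan's own figure.** n = 2 × ((1.96 + 0.84) × 0.97 / 0.7)² = 30.1, so 31 per group. This matches section 9.

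**2. Power as planned.** SE = 0.97 × √(1/40 + 1/45) = 0.211 D. Power at 0.7 D is 90.7% for an unadjusted t-test and about 89% for Mann-Whitney by simulation. Both exceed the planned 80%, so the study is not short of power.

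**3. Power with adjustment.** The share of change variance explained is R² = (L × 2.5 / 0.97)². The residual SD is 0.97 × √(1 − R²). Power uses the noncentral t with two covariate degrees of freedom.

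| L | R² | Residual SD (D) | ANCOVA power at 0.7 D |
|---|---|---|---|
| 5% | 0.017 | 0.962 | 91.1% |
| 10% | 0.066 | 0.937 | 92.4% |
| 15% | 0.149 | 0.895 | 94.5% |
| 20% | 0.266 | 0.831 | 96.9% |

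**4. Type I error if one arm is 3.5 years younger.** The baseline difference is 3.5 × 0.2 = 0.7 D. Bias in the change score is 0.7 × L. Type I error is 1 − [Φ(1.96 − bias/SE) − Φ(−1.96 − bias/SE)].

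| L | Bias (D) | Bias/SE | Unadjusted type I error |
|---|---|---|---|
| 5% | 0.035 | 0.17 | 5.3% |
| 10% | 0.070 | 0.33 | 6.3% |
| 15% | 0.105 | 0.50 | 7.9% |
| 20% | 0.140 | 0.66 | 10.2% |

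Simulation of the Mann-Whitney test (4,000 runs per case) gave 5.4, 6.6, 7.0 and 9.8%. ANCOVA with baseline and age gave 4.8-5.1%.

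**5. Chance imbalance alone.** The 95% range for a chance baseline difference is ±1.96 × 2.5 × √(1/40 + 1/45) = ±1.06 D, which multiplied by L shifts the estimate by up to 0.05-0.21 D. This variation is already inside the 0.97 D SD. With no systematic imbalance, the simulated Mann-Whitney type I error was 4.4-5.5%. The shift is lost precision, not bias.

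**6. What adjustment cannot reach.** Suppose an unmeasured factor differs by 0.5 SD between arms and correlates 0.4 with the change. Its bias is 0.5 × 0.4 × 0.97 = 0.19 D. Simulation gave about 0.20 D with or without ANCOVA, and type I error of 15% for Mann-Whitney and 17% for ANCOVA.

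**The case against.** The plan is not blind to age. The outcome is already a change score and age bands are defined in advance. Mann-Whitney applies only to non-normal data, and outcomes are recorded and summarised in dioptres. Power is ample. No baseline table is given, so imbalance is a risk and not a finding, and the figures above rest on assumed inputs. At a 5% loss the inflation is negligible. All of this stands and limits the severity of the point.

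ANCOVA is also not uniformly better when groups are not randomised. If the arms truly differ at baseline and baseline is measured with error, the change score can be unbiased while ANCOVA is not. With an assumed true baseline difference of 1 D unrelated to age and measurement-error SD of 0.3-0.65 D, ANCOVA showed bias of 0.03-0.15 D and type I error of 6-11%, while the change score stayed near 5%. This is a reason to keep the change-score analysis beside the adjusted one, not to omit adjustment.

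A reader might infer that ANCOVA would remove the confounding at no cost. The documents do not support that. Foreseeable assignment can also select on factors that are not recorded, and section 5.2 lists loss to follow-up as an exclusion. Under strict alternation starting with resection, 45 analysed plication patients imply at least 45 assigned to resection, yet 40 were analysed. Either at least 5 are absent from the analysis or alternation was not followed; regression on baseline and age repairs neither. Nor do the documents show that selection took place.

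**Conclusion.** The point holds as an omission in the plan: a non-randomised primary comparison is left unadjusted for two recorded variables, one of which the plan itself treats as relevant, and no two-group test is named for normal data. It should be corrected, but it does not show that the result is biased.

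Under the assumed baseline SD and proportional loss, unadjusted type I error is about 5-10%, against about 5% adjusted, if one arm is 3.5 years younger. Power at 0.7 D goes from about 89% to 91-97%. If change is unrelated to baseline and age, there is almost nothing to gain. A reader might take the 0.05-0.21 D chance shift as confounding; it is imprecision, and the unadjusted test keeps its error rate.

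**What to change.** Make the main between-group analysis an ANCOVA of operated-eye week-1 amplitude on arm, baseline operated-eye amplitude and continuous age, with linearity in age checked and robust or bootstrap standard errors. Report the adjusted difference in dioptres with a 95% CI, whatever the outcome of the normality test. Keep the change-score Mann-Whitney, with a Hodges-Lehmann interval, as a sensitivity analysis.

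Label the ANCOVA as specified after the study period: the document is dated 15 August 2025 and the study period ended in July 2025. Account for all allocated patients. State that the model adjusts only for measured baseline amplitude and age, so bias from non-random allocation and post-allocation exclusions can remain.

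The cost is some SAP wording, one regression on data already collected, two degrees of freedom and added modelling assumptions. The standard error also widens if the covariates differ by arm: by 1/√(1 − 0.1) = 1.05 or 1/√(1 − 0.2) = 1.12 if they explain 10% or 20% of arm membership, before any gain from the outcome variance they explain.

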Medial rectus resection has traditionally been used as a strengthening procedure. Medial rectus plication is an alternative strengthening technique in which the muscle is folded and sutured without complete disinsertion from its scleral insertion. Plication may preserve anterior ciliary vessels and adjacent neurovascular structures more effectively than resection. Because the anterior ciliary arteries and related neural pathways contribute to anterior segment physiology and ciliary muscle function, the surgical technique may influence postoperative accommodation.

The purpose of this study is to compare medial rectus resection and medial rectus plication, each combined with lateral rectus recession, with respect to postoperative accommodative changes and surgical outcomes in patients with primary exotropia.

3. Objectives

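### The trial is sized on a 0.7 D difference in mean change, but Section 10 lets a normality test choose the analysis and never plans a between-arm difference with a confidence interval

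*Combined protocol and SAP*

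**What the plan says.** Section 9 bases the sample size on operated-eye change from baseline to week 1, with "an anticipated mean difference of 0.7 diopters, and a common standard deviation of 0.97 diopters". The inputs are a difference in means and one SD for both arms.

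Section 10 applies Shapiro-Wilk to continuous variables and lets the result decide. Normal variables are summarised by mean and SD. For the others, "Non-normally distributed continuous variables will be presented as median and range". On testing: "Between-group comparisons of continuous variables will be performed using the Mann-Whitney U test when variables are not normally distributed". No between-arm test is given for the normal case. The threshold for Shapiro-Wilk, and whether it is applied per arm or to pooled data, are not stated.

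The paragraph in Section 10 on the main comparative analysis says that change will be compared within and between arms. It names no test, effect measure or interval, so the general rule above is the only one that reaches the primary outcome.

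Two other places bear on the point. Section 2 gives the biological rationale: "Plication may preserve anterior ciliary vessels and adjacent neurovascular structures more effectively than resection". Section 7.2 sets the measurement step: "Minus lenses were added over the distance correction in 0.25-diopter increments until the target could no longer be read clearly".

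**The concern.** The sample size and the analysis refer to different quantities. A trial designed to detect 0.7 D in mean change should report its estimate of that difference and how precise it is. Here a pre-test on the outcome decides whether means are shown at all.

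In the non-normal branch, a median and range per arm with a rank-test p value cannot be converted back into a mean difference. In the normal branch, which Section 9 assumes, the analyst has to supply a test that the plan does not name. A non-significant result could then not be read as excluding, or failing to exclude, 0.7 D.

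A further worry is power. If harm from resection falls on a minority of eyes, the resection arm gains a tail of losses. That makes rejection of normality more likely and moves the comparison to ranks, which give little weight to the size of those losses. How much this matters has to be calculated.

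**Working it through.** **1. The plan's own figure.** Inputs from Section 9: two-sided alpha 0.05, power 80%, difference 0.7 D, SD 0.97 D.
n per arm = 2 × (1.960 + 0.842)² / (0.7/0.97)² = 30.14, rounded up to 31. The stated 31 reproduces (31.1 with the t distribution). With the 40 and 45 patients analysed, t-test power is 90.7%.

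**2. What each branch delivers.**

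| Shapiro-Wilk | Arm summary | Between-arm test | Difference in D with CI |
|---|---|---|---|
| Rejects | Median, range | Mann-Whitney | Not planned |
| Does not reject | Mean, SD | None named | Not planned |

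This step needs no assumption about the data.

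**3. Power.** The documents do not give the distribution of change, so its shape is assumed and varied. Simulated trials had 40 v 45 eyes, values rounded to 0.25 D and a true mean difference of 0.7 D. When a share p of resected eyes carries the whole loss, each loses 0.7/p D: 2.1 D at one third, 2.8 D at one quarter, 3.5 D at one fifth. The plan's rule is read as Mann-Whitney if Shapiro-Wilk gives p < 0.05 in either arm, otherwise a t test. The threshold, its use per arm and the t test are my assumptions. Repeat runs differ by a point or two.

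| Assumed shape | Comparison | Power | Welch |
|---|---|---|---|
| Same normal shift in every eye, SD 0.97 D | Mann-Whitney | 90% | 91% |
| One third affected, noise SD 0.97 D | Plan's rule | 71% | 75% |
| One quarter affected, noise SD 0.97 D | Plan's rule | 56% | 69% |
| One fifth affected, noise SD 0.97 D | Plan's rule | 38% | 63% |
| One quarter affected, noise SD 0.45 D | Plan's rule | 53% | 93% |
| Uniform shift, heavy tails (t, 3 df), SD 0.97 D | Mann-Whitney | 99% | 91% |

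Skewed data (exponential in both arms) with a uniform shift behave much like the last row.

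**4. How these shapes sit with the common SD.** A subgroup loss adds variance p(1−p)(0.7/p)² = 0.49(1−p)/p to the resection arm.
- If both arms are to have SD 0.97 D, then 0.49(1−p)/p ≤ 0.9409, so p ≥ 0.49/(0.49 + 0.9409) = 0.342. No row with one third or fewer affected meets the plan's common SD exactly.
- With noise SD 0.97 D, the resection-arm SD becomes √(0.9409 + 1.47) = 1.55 D at one quarter affected, against 0.97 D for plication. Welch loses power too.
- The 53% v 93% row holds the average within-arm variance at 0.97². The arm SDs are then about 1.29 D and 0.45 D.
- With a true common SD of 0.97 D and 40% affected, the rule has 84% against 91% for Welch; at 50% affected, 90% against 91%.

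**5. How often the gate fires on normal data.** Shapiro-Wilk rejects in at least one arm in about 15% of trials. Two tests at 5% alone give 1 − 0.95² = 9.75%; rounding to 0.25 D adds the rest.

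**6. A responder count at 0.75 D.** A change below −0.625 D is recorded as −0.75 D or worse. With no true effect and SD 0.97 D, P(Z < −0.625/0.97) = P(Z < −0.644) ≈ 26%.

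**The case against.** Mann-Whitney on change scores is a defensible test. It costs almost nothing under a uniform normal shift and wins with heavy tails or skew, where the gate picks the more powerful test. Section 2 says only that technique may matter; nothing in the documents says that loss is confined to a minority of eyes. The widest power gap needs unaffected eyes with an SD of 0.45 D, well below the plan's 0.97 D. The planned range would show the worst loss in each arm, so a severe tail would not be invisible. In the normal branch, a reader could also rebuild the difference and an interval from the arm means, SDs and numbers.

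Most of this stands. It removes any general case against the rank test and any claim that the plan has no way of showing a large individual loss. It does not supply the missing test in the normal branch or the missing effect estimate. In the non-normal branch, the mean difference cannot be recovered from what is reported.

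**Conclusion.** The point holds as a gap in estimation and pre-specification. As written, Section 10 lets the outcome data choose between two summaries, names a between-arm test for only one of them, and plans no between-arm difference in dioptres with an interval in either. This follows from the text alone.

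The effect on power is conditional. With noise SD 0.97 D, the rule trails a comparison of means by 4 points (one third of resected eyes affected), 13 points (one quarter) and 25 points (one fifth). It makes no material difference for a uniform normal shift, and Mann-Whitney leads by about 8 points for heavy-tailed data. The share affected, the noise and the reading of the unstated branch are assumptions.

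A reader might infer that the normality gate works against the trial's hypothesis, or that it would hide an average loss of 0.7 D under the plan's own inputs. The documents do not support this. They give no pattern of loss, and the scenarios with large gaps depart from the common SD in Section 9.

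**What to change.** In Section 10, for operated-eye change in accommodative amplitude:

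- Whatever Shapiro-Wilk shows, report the between-arm difference in mean change in dioptres with a 95% CI (Welch or bootstrap). Put week 1, the sizing endpoint, first.
- Report Mann-Whitney beside it in all cases, so that the normality test no longer chooses the analysis.
- Add quartiles to the median and range; keep the range, because it shows the worst loss.
- Show the distribution of change in each arm. This is preferable to a count of eyes losing 0.75 D or more: the documents give no threshold for individual loss, and about 26% of unaffected eyes would reach that one by variation alone.
- Label these additions with their date. The study period ended in July 2025 and the document is dated 15 August 2025.

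The cost is a few sentences and a few lines of SPSS output on measurements that the plan already collects. The one downside is that a mean is more sensitive to an aberrant reading, which the rank test beside it would show.
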